25.1 APPENDIX I. List of Acronyms and Abbreviations

AAD	Antiarrhythmic drug	ICF	Informed consent form
ACT	Activated clotting time	IFU	Instructions for use
AE	Adverse event	IRB	Institutional Review Board
AF	Atrial fibrillation	ITT	Intent-to-treat
AFL	Atrial flutter	HIPAA	Health Insurance Portability and Accountability Act
AHA	American Heart Association	LA	Left atrium
ANOVA	Analysis of variance	MI	Myocardial infarction
AT	Atrial tachycardia	MRI	Magnetic resonance imaging
AV	Atrioventricular	MV	Mitral valve
BP	Blood pressure	NSC	Non-study catheter
CCS-SAF	Canadian Cardiovascular Society-Severity of Atrial Fibrillation	PAF	Paroxysmal atrial fibrillation
CEC	Clinical Events Committee	PCI	Percutaneous coronary intervention
CHF	Congestive heart failure	PIU	Patient Interface Unit
CF	Contact force	PP	Per protocol
CFAE	Complex fractionated atrial electrogram	PV	Pulmonary vein
CHADS	Congestive heart failure , H igh blood pressure, A ge 75+, D iabetes, previous S troke or transient ischemic attack	PVI	Pulmonary vein isolation
CPVI	Complete pulmonary vein isolation	QOL	Quality of life
CRF	Case Report Form	RA	Right atrium
CS	Coronary sinus	RF	Radiofrequency
CT	Computed tomography	SADE	Serious adverse device effect
CTI	Cavotricuspid isthmus	SAE	Serious adverse event
CVA	Cerebrovascular accident	SAP	Statistical analysis plan
DMC	Data Monitoring Committee	SF	Surround Flow
ECAS	European Cardiac Arrhythmia Society	SOC	Standard of care
EPU	External processing unit	SOP	Standard operating procedure
ESC	European Society of Cardiology	SVC	Superior vena cava
FDA	Food Drug Administration	TIA	Transient ischemic attack
GCP	Good Clinical Practice	TEE	Transesophageal echocardiogram
ECG	Electrocardiogram	TTE	Transthoracic echocardiogram
EHRA	European Heart Rhythm Association	TTM	Transtelephonic monitoring
HRS	Heart Rhythm Society	UADE	Unanticipated adverse device effect
ICD	Implantable cardioverter defibrillator	USADE	Unanticipated serious adverse device effect
ICE	Intracardiac echocardiography	VT	Ventricular tachycardia

[figure not shown]
CCI

[figure not shown]
CCI

CCI

CCI

25.3 APPENDIX III. Study Definitions

Term	Definition
Adverse Event (AE)	
Any unfavorable and unintended sign, medical occurrence, disease or injury (including abnormal laboratory findings) in subjects, users or other persons temporally associated with the use of a medicinal product or device whether or not related to the sponsor's product.
 
This definition includes events related to the medical device and/or the comparator, and events related to the procedure in which the device was used.

Adverse Device Effects (ADE's)	Adverse events related to the use of the medical device. This definition includes adverse events resulting from insufficient or inadequate instructions for use deployment, implantation, installation, or operation, or any malfunction of the medical device. This definition includes any event resulting from use errors or from intentional misuse of the investigation medical device.
AF/AT/AFL of unknown origin Episode	An episode of AF/AT/AFL of unknown origin ⁺ ≥ 30 seconds in duration.
AF Episode	An atrial fibrillation episode is defined as AF which is documented by ECG monitoring and has a duration of at least 30 seconds, or if less than 30 seconds, is present continuously throughout the ECG monitoring tracing. The presence of subsequent episodes of AF requires that sinus rhythm be documented by ECG monitoring between AF episodes
Anticipated AE	An effect which by its nature, incidence, severity or outcome has been identified as possible complications associated with the medical device and/ or intervention procedure.
Atypical Flutter	Macro-reentrant circuits within the atria where activation rotates around large obstacles that does not meet the criteria for Typical Flutter.

Term	Definition
Bleeding Complications (ISTH definition):	
Major (ISTH definition):
 
Fatal bleeding AND/OR symptomatic bleeding in a critical area or organ, such as intracranial, intraspinal, intraocular, retroperitoneal, intraarticular, pericardial, or intramuscular with compartment syndrome AND/OR bleeding causing a fall in hemoglobin level of 2 g/dL (1.24 mmol/L) or more, or leading to transfusion of two or more units of blood.
 
Clinically relevant nonmajor bleed (ISTH definition):
 
An acute or subacute clinically overt bleed that does not meet the criteria for a major bleed but prompts a clinical response such that it leads to one of the following: hospital admission for bleeding; physician guided medical or surgical treatment for bleeding; change in antithrombotic therapy (including interruption or discontinuation).
 
Minor bleeding (ISTH definition):
 
All nonmajor bleeds. Minor bleeds are further divided into clinically relevant and not.

Catheter Insertion	Defined as the VARIPULSE™ Catheter breaching the sheath and entering the bloodstream.
Device Deficiency	Inadequacy of a medical device related to its identity, quality, durability, reliability, safety or performance, such as malfunction (failure of a medical device to perform in accordance with its intended purpose when used in accordance with the instructions for use or protocol), misuse or use error and inadequate labeling.
Documented AF/AT/AFL of unknown origin episode	An AF/AT/AFL of unknown origin ⁺ episode documented by an electrocardiographic monitoring tool. This may include ILR, ECG, TTM, Holter monitor, or telemetry strip. Reporting of a symptomatic episode by a patient or in a referral letter is not considered a documented AF episode.
Minor Pericarditis	Pericarditis will be considered 'minor' if it is treated using only analgesics and does not extend hospitalization by more than 48 hours.
Paroxysmal AF	Paroxysmal AF is defined as recurrent AF (≥ 2 episodes) that terminates spontaneously within 7 days. Episodes of AF of ≤ 48 hours duration that are terminated with electrical or pharmacologic cardioversion should also be classified as paroxysmal AF episodes.

Term	Definition
Permanent AF	Not appropriate in the context of patients undergoing catheter ablation of AF; refers to a group of patients where a decision has been made not to pursue restoration of sinus rhythm by any means, including catheter or surgical ablation.
Persistent AF (PsAF)	Persistent AF is defined as continuous AF that is sustained beyond 7 days and less than 1 year.
Serious adverse event (SAE)	
1. Any adverse event that:
 
 • Led to a death • Led to a serious deterioration in health that either: 
 ○ Resulted in a life-threatening illness or injury, or ○ Resulted in a permanent impairment of a body structure or a body function, or ○ Required in-patient hospitalization or prolongation of existing hospitalization, or ○ Resulted in medical or surgical intervention to prevent life threatening illness or injury or permanent impairment to a body structure or a body function • Led to fetal distress, fetal death or a congenital abnormality or birth defect 
2. Any Device Deficiency that could have led to an SAE
 
A planned hospitalization for pre-existing condition, or a procedure required by the protocol, without a serious deterioration in health, is not considered to be a serious adverse event.
 
Medical and scientific judgment should be exercised in deciding whether expedited reporting is appropriate in other situations, such as important medical events that may not be immediately life-threatening or result in death or hospitalization but may jeopardize the subject or may require intervention to prevent one of the outcomes listed in the definition above.

Serious Adverse Device Effects (SADEs)	Adverse device effects that have resulted in any of the consequences characteristic of a serious adverse event.
Symptomatic AF/AT/AFL of unknown origin[†] Episode	Symptom(s) which is/are exhibited by the subject which made them seek medical attention and are concurrent with a documented episode of AF/AT/AFL by either ECG, TTM, Holter monitor, or telemetry recording. Symptoms may include but are not limited to: palpitations, irregular pulse (e.g., rapid, racing, pounding, fluttering, bradycardia), dizziness, weakness, chest discomfort, and breathlessness.

Term	Definition
Typical Flutter	Atrial flutter is caused by a reentrant rhythm in either the right or left atrium. Typically initiated by a premature electrical impulse arising in the atria, atrial flutter is propagated due to differences in refractory periods of atrial tissue. This creates electrical activity that moves in a localized self-perpetuating loop. For each cycle around the loop, there results an electric impulse that propagates through the atria.
Unanticipated Serious Adverse Device Effect (USADE)	Serious adverse device effect which by its nature, incidence, severity or outcome has not been identified in the current version of the risk analysis report. NOTE: Anticipated SADE: an effect which by its nature, incidence, severity or outcome has been previously identified in the risk analysis report
Ventricular Tachycardia (VT)	Ventricular tachycardia: a tachycardia (rate $\geq 100/\text{min}$) with three or more consecutive beats that originates from the ventricles independent of atrial or AV nodal conduction. Continuous VT for $\geq 30\text{ s}$ or that requires an intervention for termination (such as cardioversion).

[†]AFL of unknown origin is defined as all AFL except those CTI dependent AFL as confirmed by 12-Lead ECG and entrainment maneuvers in an EP study.

APPENDIX IV. Anticipated Adverse Events

(Acute) renal failure	Infection, systemic
(Aspiration) pneumonia	Inflammation
(Skin) laceration	Isolated ST segment elevation
(Vascular) bleeding	Liver toxicity
Acute Respiratory Distress Syndrome (ARDS)	Local Hematoma/ecchymosis
Air embolism	Localized skin reaction
Allergic reaction to contrast media	Mitral Insufficiency
Allergic skin reaction	Myocardial infarction with or without ST elevation
Altered Mental Status Confusion; Altered Level of Consciousness;	Nausea
Anaphylactic shock	Neurological disorders (poor coordination)
Anemia	Neurological disorders (tremor)
Anesthesia complications/reactions	Neuropaxia/Muscle contraction
Anoxic or hypoxic encephalopathy	Palpitations
Aortic Puncture	Papillary Muscle tear/injury
Apnea - sedation induced	Pericardial effusion resulting in tamponade
Arrhythmia (new or worsening of pre-existing arrhythmia)	Pericardial effusion without tamponade
Asthmatic attack	Pericarditis
Asymptomatic Cerebral Emboli	Periesophageal vagal nerve injury
Atelectasis	Peripheral nerve injury
Atrial fibrillation	Phlebitis
Atrial Septal Defect (acquired)	Phrenic nerve damage/injury
Atrio-Esophageal fistula	Pleural effusion
Auditory Disorder	Pneumothorax
AV fistula	Post- and perioperative pain
Back Pain	Post Procedural Hematuria
Bone disorder	Pseudoaneurysm
Bronchial fistula, Broncho-pericardium fistula	Pulmonary edema
Cardiac arrest	Pulmonary embolism
Cardiac pacemaker insertion or replacement	Pulmonary hypertension
Cardiac perforation	Pulmonary toxicity, like acute pulmonary syndrome
Cardiac Valve Rupture/Damage	Pulmonary vein dissection
Cardiogenic Shock	Pulmonary vein stenosis
Cerebro-Vascular accident (CVA)/Stroke	Renal Artery Stenosis
Chest pain/discomfort	Respiratory arrest
Complete or incomplete heart block	Respiratory depression

Conduction block	Respiratory failure
Coronary Artery Stenosis	Respiratory infection
Coronary artery thrombosis	Retinal Artery Embolism
Death	Retroperitoneal bleeding
Deep venous thrombosis	Rhabdomyolysis, including produced by body position or propofol
Diaphragmatic paralysis	Sedation induced CO ₂ retention with lethargy and cholecystitis
Dislodgement/Malfunction of pacemaker/defibrillator leads	Seizure
Disseminated Intravascular Coagulation	Sepsis
Dizziness, presyncope, vertigo	Sinus bradycardia
Dysphagia	Sinus tachycardia
Dyspnea	Skin burn or necrosis
Endocarditis	Skin discoloration
Epigastric Distress	Skin edema
Epistaxis	Skin or soft tissue (radiation) injury/tear
Esophageal injury / perforation	Subclavian artery puncture
Expressive aphasia	Temperature elevation / Fever
Fatigue	Thrombocytopenia
Gastric hypomotility	Thromboembolism
Gastroesophageal reflux	Thrombosis
Gastrointestinal disorders	Thyroid disorders
Gastrointestinal diverticulosis	Toxic reaction
Gastroparesis	Transient extremity numbness
Headache	Transient Ischemic attack (TIA)
Heart failure (acute or chronic)	Urinary Retention Postoperative
Heart injury	Urinary tract injury or infection related to the urinary catheter
Heart valve insufficiency	Valvular damage/insufficiency
Hemoptysis	Vascular (access) dissection (including coronary arteries)
Hemorrhage	Vascular occlusion
Hemothorax	Vasovagal reactions
High/increased creatine phosphokinase (CPK)	Ventricular Fibrillation
Hypertension	Vessel damage/trauma
Hypervolemia	Vessel perforation
Hypotension	Vessel spasm (including coronary arteries)
Hypovolemia	Visual disturbance
Hypoxia	Worsening of pre-existing pulmonary disease
Increased phosphokinase level	Wound healing disturbance
Infection, localized	

*Atrial Fibrillation and exacerbation of an existing arrhythmia are anticipated adverse events. However, they will not be captured as such under this protocol, as they are considered recurrence of disease.

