14.1 Adverse Event Recording

An adverse event is any untoward medical occurrence, unintended disease or injury, or untoward clinical signs (including abnormal laboratory findings) occurring during a clinical study, whether or not related to the study device or ablation procedure.

The following clinical events will not be considered an adverse event for this clinical study:

- Any medical condition that is present at the time of screening. Such conditions should be added to the medical history if not previously reported. However, if the study subject's condition deteriorates at any time during the study, it should be recorded as an AE.

The following clinical events will not be considered an adverse event for this clinical study but will be captured in the database separately:

- Recurrence of pre-existing AF/AT/AFL of unknown origin⁺
- AF/AFL of unknown origin⁺/AT recurrence requiring direct current cardioversion during the blanking period or pharmacological cardioversion (and accompanying hospitalization) at any

time throughout the duration of the study. However, new onset of left atrial flutter occurring post-ablation is an AE. For subjects with AFL recurrence identified through TTM and/or Holter monitoring, a 12 Lead ECG MUST be collected.

- Re-ablation for AF or pre-existing AFL of unknown origin⁺/AT (including accompanying hospitalization) itself is not an AE, however any complication associated with the repeat ablation procedures is considered an AE and shall be reported within the applicable timelines.

Subjects should be encouraged to report AEs spontaneously or in response to general, non-directed questioning (e.g., "How has your health been since last visit?"). Anytime during the study, the subject may volunteer information that resembles an AE.

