Stroke/ Cerebrovascular Accident	
Rapid onset of a focal or global neurological deficit with at least one of the following: change in level of consciousness, hemiplegia, hemiparesis, numbness or sensory loss affecting one side of the body, dysphasia or aphasia, hemianopia, amaurosis fugax, or other neurological signs or symptoms consistent with stroke.
 
Duration of a focal or global neurological deficit ≥ 24 h; or < 24 h, if therapeutic intervention(s) were performed (e.g., thrombolytic therapy or intracranial angioplasty); OR available neuroimaging documents a new hemorrhage or infarct; or the neurological deficit results in death.
 
No other readily identifiable non-stroke cause for the clinical presentation (e.g., brain tumor, trauma, infection, hypoglycemia, peripheral lesion, pharmacological influences)†
 
Confirmation of the diagnosis by at least one of the following:
 
• Neurology or neurosurgical specialist• Neuroimaging procedure (MR or CT scan or cerebral angiography)• Lumbar puncture (i.e., spinal fluid analysis diagnostic of intracranial hemorrhage) 
Stroke: (diagnosis as above, preferably with positive neuroimaging study)
 
• Minor—Modified Rankin score < 2 at 30 and 90 days††• Major—Modified Rankin score ≥ 2 at 30 and 90 days
Thromboembolism	Formation of a clot (thrombus) inside a blood vessel causing obstruction to blood flow. The thrombus can migrate (embolus) and obstruct distal vascular sites. Diagnostic tests to help detect thromboembolisms may include but are not limited to angiography (pulmonary or distal), ventilation-perfusion (V/Q) scans, venography, Doppler ultrasonography, spiral CT, and echocardiography. For the purposes of this study, silent (asymptomatic) cerebral embolism will not be considered a PAE.
Transient Ischemic Attack	New focal neurological deficit with rapid symptom resolution (usually 1 to 2 h), always within 24h. Neuroimaging without tissue injury.
Phrenic Nerve Injury / Diaphragmatic Paralysis	Absent phrenic nerve function as assessed by a sniff test. A phrenic nerve paralysis is considered to be permanent when not resolved at the final follow-up.

PRIMARY ADVERSE EVENT	DESCRIPTION / CRITERIA
Heart Block	Impairment of AV conduction requiring intervention (e.g., temporary or permanent pacemaker) due to iatrogenic cause (e.g., inappropriate RF application, traumatic maneuvering of catheter or other intracardiac devices).

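### The Appendix IV footnote excludes worsening of an existing arrhythmia from adverse event capture, which is broader than the exemption in Protocol Section 14.1

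*Protocol*

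**What the plan says.** Three places in the protocol bear on whether a worsening arrhythmia is recorded as an AE.

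- **Appendix IV, footnote.** "Atrial Fibrillation and exacerbation of an existing arrhythmia are anticipated adverse events". It then continues: "However, they will not be captured as such under this protocol, as they are considered recurrence of disease". It does not say which arrhythmias it covers, or that the events are captured anywhere else.
- **Section 14.1.** A condition present at screening is not an AE. If the subject's "condition deteriorates at any time during the study, it should be recorded as an AE". The arrhythmia exemptions stand in a separate list, introduced by "The following clinical events will not be considered an adverse event for this clinical study but will be captured in the database separately". The first item is "Recurrence of pre-existing AF/AT/AFL of unknown origin". The second is such recurrence "requiring direct current cardioversion during the blanking period or pharmacological cardioversion (and accompanying hospitalization) at any" time in the study. The third is re-ablation for AF or for pre-existing AT or AFL of unknown origin. New left atrial flutter after ablation is named as an AE. The section ends by requiring every AE that meets its definitions to be recorded.
- **Appendix IV, list.** One entry reads "Arrhythmia (new or worsening of pre-existing arrhythmia". Section 14.2.4 sends sites to this list and tells them to report a listed event as anticipated.

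SAP Section 8.4.3.1 makes SAE incidence by time window an additional safety endpoint. SAP Section 8.13.1 has it summarised descriptively, with no hypothesis test.

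**The concern.** A site with a subject whose pre-existing arrhythmia worsens finds two rules. If the arrhythmia is not AF, AT or AFL of unknown origin, Section 14.1 says to record an AE and the footnote says not to. Sites may settle this differently, and where they follow the footnote the event leaves the AE and SAE tables.

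The trial has a single arm, so there is no control group in which under-recording would show. The additional safety results describe the device's harm profile for a premarket submission. A definition that varies by site makes them hard to interpret and biases them downward.

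**Working it through.** No figure in the plan depends on this point, so the check is a comparison of the rules, event by event.

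| Event in a subject | Section 14.1 | Appendix IV footnote | Agree? |
|---|---|---|---|
| Recurrence of pre-existing AF, AT or AFL of unknown origin | Not an AE; captured separately | Not an AE | Yes |
| Worsening of pre-existing CTI-dependent flutter | AE (deterioration clause) | Not an AE | No |
| Worsening of a pre-existing ventricular arrhythmia | AE (deterioration clause) | Not an AE | No |
| AF/AT/AFL recurrence needing DC cardioversion in the evaluation period | Recurrence exempt, but the DC cardioversion exemption covers only the blanking period | Not an AE | Unclear |
| New left atrial flutter | AE | Not covered (not an existing arrhythmia) | Yes |

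**Can the conflicting rows occur?** Yes.

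- Exclusion 4 in Section 10.2 removes patients known to need ablation outside both the PV ostia and the CTI region, so a need for CTI ablation does not exclude. The procedure description in the synopsis allows CTI ablation when typical flutter was documented before or during the procedure. Subjects with CTI-dependent flutter can therefore be enrolled.
- Table 12.1.1.1 names ventricular arrhythmias as the reason for Class I or III drug use other than AF, so the plan foresees them too.

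**Where else would worsening CTI-dependent flutter be counted?** Once confirmed, it is outside the primary effectiveness endpoint, which counts only AFL of unknown origin. Section 13.4 says procedures for it during follow-up are not repeat procedures. It is not among the Section 14.1 events that are captured separately. Section 13.5 does collect AFL recurrence at visits, so the rhythm finding need not be lost. What is lost under the footnote is its status as an AE.

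**Does that reach the SAE count?** Appendix III defines an SAE as an adverse event meeting a seriousness criterion. An event that is not captured as an AE is therefore not counted as an SAE, even if it leads to admission. The effect runs in one direction: SAE incidence is understated.

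**The case against.** The best defence is that the footnote limits itself through its reason. The disease under study is AF, and worsening of a ventricular arrhythmia is not recurrence of that disease. On this reading the footnote only restates Section 14.1 loosely. Section 14.1 is also the recording rule, while Section 14.2.4 uses Appendix IV only to classify events as anticipated. As an account of what the sponsor probably meant, this stands. It does not cure the wording: the footnote names an existing arrhythmia without restriction and declares it to be recurrence. A site could readily treat CTI-dependent flutter that way in a subject with AF.

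A reader might also infer more than the documents support.

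- **That the primary safety test is at risk through heart block.** Table 14.2.1.1 defines this event as "Impairment of AV conduction requiring intervention" with an iatrogenic cause, which is procedural injury and not worsening of an existing arrhythmia. Heart block and conduction block are separate entries in Appendix IV, and Section 14.2 requires immediate reporting of primary AEs and of any hospitalization. No link to the comparison with the 12% goal is shown.
- **That arrhythmia from vagal responses goes unrecorded.** Section 6.4 describes this as induced by the procedure. It is a new event, and the footnote does not reach it.
- **That unanticipated device effects are hidden.** Section 14.2.5 requires an effect not already identified in nature, severity or degree of incidence. Worsening arrhythmia is listed as anticipated, so any effect is marginal.
- **That a number of missing events can be given.** The documents contain no rate for worsening of a non-study arrhythmia. Exclusions 4 and 23 also shrink the pool, by removing patients known to need ablation for several other arrhythmias and those with a pacemaker or ICD.

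**Conclusion.** The inconsistency is real and lies in operative text. For worsening of a pre-existing arrhythmia outside the Section 14.1 exemptions, the two rules give opposite answers. CTI-dependent flutter is the clearest case and ventricular arrhythmia the second. Where sites follow the footnote, the descriptive AE and SAE results are too low by an amount that the documents do not allow one to estimate. The primary safety endpoint is largely unaffected, and no sample size, power or hypothesis test changes.

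This rests on two assumptions: that an intermittent arrhythmia in the history counts as a condition present at screening, and that at least some sites would read the footnote literally. It does not depend on which list entry carries the asterisk, which the extracted text does not show, because the footnote names its own events. The point merits correction as a clarification of event recording.

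**What to change.** Replace the footnote with a cross-reference, for example: *Events exempted in Section 14.1 (recurrence of pre-existing AF, AT or AFL of unknown origin, and cardioversion or re-ablation for it as specified there) are captured separately and not as AEs. Worsening of any other pre-existing arrhythmia is an AE and is recorded under Section 14.1.*

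Pointing to Section 14.1 keeps its cardioversion and re-ablation provisions in force. Merely deleting the reference to exacerbation would leave it open whether worsening of AF itself falls under the deterioration clause. In the same edit, the sponsor should state in Section 14.1 how a recurrence that needs DC cardioversion in the evaluation period is to be recorded.

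The cost is one sentence in the appendix, that clarification in Section 14.1 and a notice to sites, with a few more AEs reported. If subjects have already been followed under the present wording, sites should be asked whether any such event was left out on the strength of the footnote.
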